6.1.7 Any procedures for the replacement of subjects

No replacement condition is foreseen.

Drop-outs will not be replaced as it is foreseen to randomize 80 subjects for having at least 68 subjects to be analysed.

6.2 INVESTIGATIONAL DEVICE(S) AND COMPARATOR(S)

6.2.1 Description of the exposure to the investigational device(s) or comparator(s), if used

6.2.1.1 Dosage

[figure not shown]
For both investigational medical device (DM05) and comparator (Optive®), one to two drops will be instilled in each eye from 4 to 6 times per day.

6.2.1.2 Instructions for use

DM05:

Wash hands carefully before application.

1. For the first application, verify that the cap seal is not broken and unscrew the cap. You will hear the tamper-proof ring when it breaks for the first time.
2. Always shake the vial before application.
3. Apply 1 to 2 drops from 4 to 6 times per day. With your index finger, draw the lower eyelid gently downwards, while looking up, and then squeeze the vial to apply the eye drops. Do not touch the eyes or eyelids with the tip of the vial. After application, spontaneous blinking will evenly distribute the emulsion over the surface of the eye, creating a transparent and durable film.
4. Seal the vial with the protective cap after every use.

Optive®

Instil one to two drops in each eye from 4 to 6 times per day.

6.2.1.3 Precautions for use

DM05:

- For external use only.
- Do not swallow.
- Store at room temperature (below 25°C).
- Wash hands carefully prior to instillation.
- Always shake the vial before application.
- Do not touch the tip of the vial with hands, eyes or eyelids (risk of microbial contamination).
- Replace the protective cap on the tip of the vial after every use (risk of microbial contamination).

Horus Pharma	CIP #15E1122	Final Version 4.0 Date: 04/09/2017	Confidential Page 25/53
--------------	--------------	---------------------------------------	----------------------------

- Do not use if the vial is damaged (risk of microbial contamination).
- Maintain a minimum interval of 15 minutes between administration of two ophthalmic products.
- Do not use after the expiry date stated on the vial and the package (risk of microbial contamination).
- Keep out of reach and sight of young children.

Optive®

- Do not use if you are allergic to one of the constituent.
- Do not swallow.
- To avoid any contamination, ensure that the dropper does not touch any surface and avoid any direct contact with the eye.
- Carefully close the bottle after use.
- Do not use after the expiry date stated on the bottle
- Keep out of reach of children.
- Keep at room temperature.
- Do not use the bottle if the inviolability cap on the bottle neck is damaged before the first use of the product.
- Respect at least 5 minutes between administration of two ophthalmic products.

6.2.2 Justification of the choice of comparator(s)

Optive®, number two on the French market of medical devices indicated for moderate to severe ocular dryness with 28% of market share (source : GERS- May 2016) and part of the European leaders in ocular dryness is the chosen comparator.

6.2.3 List of any other medical device or medication to be used during the clinical investigation

All patients will be given preservative free artificial tears during the wash-out period.

- **Name of the auxiliary product:** HYDRABAK® (NaCl 0.9%)
- **Composition:**

Name of the ingredients	Centesimal formula (g): 10 mL vial
Active ingredient	
Sodium chloride	0.090 g
Other ingredients	
Sodium dihydrogen phosphate dihydrate	0.0067 g
Disodium phosphate dodecahydrate	0.0317 g
Water for injections	ad 10 mL

- **Form:** Hydrabak® is unpreserved NaCl 0.9 % eye drops, coming from commercially purchased batches. Hydrabak® is to be used within 8 weeks after opening and stored at temperatures below 25°C.
- **Instructions for use**
1 instillation in both eyes 3 times per day.
Instillation of preservative-free artificial tears should not be performed within the 6 hours prior to the D0 visit.

6.2.4 Number of investigational devices to be used, together with a justification

DM05: Each subject will receive 2 vials of 10 ml.
Optive: each subject will receive 2 vials of 10 ml

6.3 STUDIED POPULATION

6.3.1 Inclusion criteria for subject selection

- Sex: male or female.
- Age: more than 18 years.
- Subject with a dry eye syndrome needing artificial tears in the 3 months preceding the inclusion.
- Subject having used only artificial tears without preservative (NaCl 0.9%, Hydrabak®) during 1 to 2 weeks before inclusion (at 3 drops per day).
- Diagnosis of moderate to severe ocular dryness defined by a score OSDI (Ocular Surface Disease Index) ≥ 18 .
- Subject with at least one eye with
 - Global ocular staining (cornea and conjunctiva) ≥ 4 and ≤ 9 (Oxford scale from 0 to 15)
- **AND** one the following criteria:
 - Schirmer test ≥ 3 mm/5 min and ≤ 9 mm/ 5 min
 - **OR**
 - Sum of 3 measurements of Tear film Break-Up Time (TBUT) ≤ 30 s.
- Subject, having given freely and expressly his/her informed consent.
- Subject who is able to comply with the study requirements, as defined in the present protocol, at the Investigator's appreciation.
- In France: subject being affiliated to a health social security system.
- Female subjects of childbearing potential should use a medically accepted contraceptive regimen since at least 12 weeks before the beginning of the study, during all the study and at least 1 month after the study end.

6.3.2 Exclusion criteria for subject selection

- Pregnant or nursing woman or planning a pregnancy during the study.
- Subject who had been deprived of their freedom by administrative or legal decision.
- Subject in a social or sanitary establishment.
- Major subject who is under guardianship or who is not able to express his consent.
- Subject being in an exclusion period for a previous study.
- Subject suspected to be non-compliant according to the Investigator's judgment.
- Subject wearing contact lenses during the study.
- Far best corrected visual acuity $< 1/10$.
- Subject with severe ocular dryness with one of these conditions:
 - Eyelid or blinking malfunction
 - Corneal disorders not related to dry eye syndrome
 - Ocular metaplasia
 - Filamentous keratitis
 - Corneal neovascularization
- Subject with severe meibomian gland dysfunction (MGD).
- Within the last 3 months prior to the inclusion, history of ocular trauma, infection or inflammation not related to dry eye syndrome.
- Within the last 12 months, history of ocular allergy or ocular herpes.
- History of inflammatory corneal ulcer, recurrent corneal erosion, uveitis.
- Refractive or cataract surgery within the last 6 months.
- Any laser other than refractive surgery within the last 3 months.
- Any troubles of the ocular surface not related to dry eye syndrome.
- Ocular hypertension or glaucoma needing an hypotonic treatment
- Subject having used artificial tears in the 6 hours preceding the inclusion visit.
- Use during the month preceding the inclusion or during the study of: isotretinoid, cyclosporine, tacrolimus, sirolimus, pimecrolimus. punctual plugs.
- Any not stabilized systemic treatment, which can have an effect on performance or safety criteria, at the investigator appreciation.

6.3.3 Point of enrolment

Estimated date of clinical investigation beginning: February 2017.
Estimated date of clinical investigation end: February 2018.

6.3.4 Total expected duration of the clinical investigation

13 months.

6.3.5 Expected duration of each subject's participation

84 days of treatment + 7 to 14 days of wash-out.

6.3.6 Number of subjects required to be included in the clinical investigation

80 patients are expected to be randomized in the clinical investigation: 40 patients in each group of treatment.

6.3.7 Estimated time needed to select this number in the clinical investigation (enrolment period)

9 months.

6.4 PROCEDURES

6.4.1 Description of all the clinical-investigation-related procedures that patients undergo during the clinical investigation

Selection visit (D-14 to D -7)

- The ophthalmologist will propose to his/her patient to participate to the clinical investigation.
- Information of the patient on study aims and schedule.
- Signature of information sheet and consent form in two copies by the patient and the investigator.
- Collection of previous medical and ophthalmological history, previous and actual treatments, demographic data.
- The ophthalmologist will evaluate the Ocular Surface Disease Index, the global ocular staining (Oxford score) and will realize the Schirmer test and TBUT.
- Checking of inclusion and exclusion criteria.
- If the patient is eligible, distribution of Hydrabak® to be used three times per day in both eyes until the inclusion visit, as well as a daily log to write eventual concomitant treatments and adverse events.

Inclusion visit (D0)

- The patient will bring back the Hydrabak® and the daily-log completed.
- Collection of adverse events and concomitant treatments.
- The ophthalmologist will evaluate the Ocular Surface Disease Index, the global ocular staining (Oxford score) and will realize Schirmer test and TBUT.
- Checking of inclusion and exclusion criteria.
- If the patient is eligible, inclusion of the patient and attribution of a randomization number.
- The ophthalmologist will evaluate the Van Bijsterveld score.
- The patient will evaluate his/her ocular symptoms.
- A third person will distribute the treatment according to the randomization list and explain the mode of use of the treatment, as well as a daily log to write eventual concomitant treatments and adverse events

D35

- The patient will bring back the treatments (used and non-used) and the daily-log completed.

- Collection of adverse events and concomitant treatments.
- The ophthalmologist will evaluate the Ocular Surface Disease Index, the global ocular staining (Oxford score), the Van Bijsterveld score and will realize Schirmer test and TBUT.
- The patient will evaluate his/her ocular symptoms.
- The patient and the investigator will evaluate the treatment performance on a 4-point scale.
- A third person will distribute the treatment according to the randomization list and remain the patient about the mode of use, as well as a daily log to write eventual concomitant treatments and adverse events.

D84

- The patient will bring back the treatments (used and non-used) and the daily-log completed.
- Collection of adverse events and concomitant treatments.
- The ophthalmologist will evaluate the Ocular Surface Disease Index, the global ocular staining (Oxford score), the Van Bijsterveld score and will realize Schirmer test and TBUT.
- The patient will evaluate his/her ocular symptoms.
- The patient and the investigator will evaluate the treatment performance on a 4-point scale.

6.4.2 Description of activities performed by Sponsor representatives (excluding monitoring)

The Sponsor has delegated the following activities to the CRO (Dermscan):

- Submission of the study files to the EC and competent authority
- Monitoring of the study
- Data management
- Statistical analysis and clinical investigation report writing.

6.4.3 Any known or foreseeable factors that may compromise the outcome of the clinical investigation or the interpretation of results

Not applicable.

6.5 MONITORING

The monitoring of the study will be done by Dermscan. The monitor has the responsibility to familiarise the Investigator(s) and the centre staff involved in the study with all study procedures if necessary. The monitor has the responsibility of reviewing the ongoing study with the Investigator(s) to verify adherence to the CIP and to deal with data queries as well as any problems that arise during the conduct of the study.

6.5.1 Monitoring visits

6.5.1.1 Selection visit

Before any involvement of a clinical research centre/private practice into the study, the CRA and/or the study monitor should perform a selection visit in order to verify:

- adequate human and technical resources,
- adequate recruitment capabilities,
- availability regarding planning constraints.

6.5.1.2 Initiation visit

Before any subject's enrolment, the CRA and/or the study monitor will conduct an initiation visit in order to familiarize the centre's staff with the study CIP and schedule.

This visit will also be the occasion to review with the center:

- the Investigator file which should contain:
 - the study CIP,

- the curriculum vitae of the Investigator,
- the Authorization as a clinical centre, if applicable,
- the insurance certificate,
- the favourable opinion of the ethic committee,
- the approval of CA,
- the Investigator brochure,
- the financial agreement between all parts,
- all necessary documents for study follow-up, etc.
- the CRF and the way to complete it,
- the information sheet and consent forms and the way to obtain consent,
- the investigational products,
- the study material (pregnancy test, etc.),
- and all other necessary aspects and materials detailed in the study CIP.

6.5.1.3 Monitoring visits

For the duration of the study, monitoring visits may be performed by the CRA in order to check the study performance in accordance with the study CIP.

The Clinical Research Associate ensures the coherence and the veracity of the data reported in the Case Report Form compared to the source data. He/she verifies that the study is performed according to the CIP and that all documentation necessary to ensure a good follow-up of the study is present and well completed.

These visits will also serve to ensure product accountability.

During these visits, the CRA reserves the right to ask for queries resolution, directly in the document(s) concerned or with specific data clarification forms. He/she ensures the completion of the Investigator file and retrieves all documents necessary for updating the trial master file.

When applicable, the CRA may retrieve duplicate of the CRF to be sent to the data management department.

6.5.1.4 Close-out visit

A close out visit will take place after the study has come to a conclusion. The CRA will retrieve all study products, materials, CRFs, consent forms (if applicable) and to confirm the completion of the Investigator file, including all study related documents. When necessary, the Sponsor may also ask for the resolution of any delayed queries in the CRFs.

6.5.2 Access to source data

In accordance with good clinical practices and the standards of the data protection law, data obtained in the course of a biomedical research has to be treated confidentially to guarantee the subjects' privacy.

The Investigator agrees that, subject to local regulations and ethical considerations, the Sponsor representatives designee and/or and any regulatory agency have direct access to all study records, CRFs, corresponding subject medical records, study drug dispensing records and study drug storage area, and any other documents considered source documentation. The Investigator also agrees to assist the representative, if required.

7- STATISTICAL CONSIDERATIONS

7.1 STATISTICAL DESIGN, METHOD AND ANALYTICAL PROCEDURES

A Statistical Analysis Plan (SAP) specifying analyses in detail will be written before blind review and locking the database.

The statistical analysis will be performed after the data has been cleaned and after the database is locked.

No interim analysis is planned.

7.1.1 Analysed population

Three populations will be defined:

- Intention to treat (ITT) population corresponding to all patients randomized
- Safety population corresponding to all patients randomized and having received at least one dose of treatment
- Per protocol (PP) population corresponding to patients of the safety population who will not present major protocol deviation (decided by the Data Review Committee during a blind review process)

7.1.2 Primary endpoint

7.1.2.1 Main analysis

The main analysis of the main criterion will be conducted on the PP population. The hypothesis of non-inferiority of DM05 compared to Optive® will be tested by calculating the bilateral 95% CI of the difference between groups (DM05 – Optive®) of the change from baseline of global ocular staining in the worse eye on Day 35. A two-way analysis of covariance (ANCOVA) model will be constructed using main effects of treatment and baseline score as covariate. Adjusted means (least square mean and error standard of the mean) by treatment will be presented as well as an estimate of the difference between adjusted means.

A 95% two-sided confidence interval, based on the ANCOVA model, will be computed for the difference of DM05 minus Optive®.

If the upper bound is no higher than 2 points for the PP population, it will be concluded that the null hypothesis can be rejected and that DM05 is non-inferior to Optive®.

The p value of non-inferiority will be expressed taking on board the predefined margin of non-inferiority.

This analysis will be based on observed cases.

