7.1.2.2 Sensitivity analysis

Same analysis will be performed on ITT population with imputation of values in case of missing data with LOCF technique (baseline value or value in case of withdrawal) and without imputation (observed cases).

In case of conclusion of non-inferiority of DM05 compared to Optive®, the superiority of DM05 compared to Optive® will be tested. The superiority analysis carried out on the ITTT population will be considered as the main analysis. Results will be also provided on the PP population.

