7.2 SAMPLE SIZE AND ITS STATISTICAL JUSTIFICATION

The primary objective of this study is to confirm the non-inferiority of DM05 in comparison with Optive™ reference for global ocular staining assessed with a 0-15 score (Oxford score). The clinical non-inferiority margin was set at 2 points on the Oxford score. Assessing a standard-deviation equal to 2.5, a total of 68 patients (34 patients in each group) is required to reach a power of 90% to set-up the non-inferiority based on a bilateral confidence interval at 95%.

Assuming a drop-out rate of 15%, 80 patients will be randomized in the study to keep sufficient power for main analysis of the primary end point (analysis on PP population).

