7.3 LEVEL OF SIGNIFICANCE AND POWER OF THE CLINICAL INVESTIGATION

All statistical tests will be assessed at $\alpha = 5\%$ level of significance in a bilateral approach.

7.4 STATISTICAL PASS/FAIL CRITERIA TO BE APPLIED TO THE RESULTS OF THE CLINICAL INVESTIGATION

Non-inferiority of DM05 versus Optive with a non-inferiority margin set at 2 points on the Oxford score.

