6.2 Generalities for statistical analyses

Continuous variables will be summarized by number of non-missing observations, mean, standard deviation, minimum, median, maximum.

Categorical data will be summarized by frequency and percentage of patients in each category. Percentages will be based on non-missing observations.

All statistical tests will be 2-tailed with a Type I error of 0.05 unless otherwise stated.

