7.1 Study Populations

7.1.1 Protocol Deviations

Definition of minor and major deviations will be provided. Number of subjects with at least one major/minor deviations will be computed.

A listing of all the protocol deviations observed during the Data Review will be provided, and protocol deviations will be summarized in tables, for the whole population.

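### Non-inferiority is concluded from the per-protocol set alone, so a failing ITT result cannot change the verdict although PP membership is settled after randomisation

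*Protocol*

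**What the plan says.** **Decision rule.** Protocol 7.1.2.1 runs the main analysis on PP, on observed cases, and states: "If the upper bound is no higher than 2 points for the PP population, it will be concluded" that DM05 is non-inferior. SAP 4.1.1 and SAP 7.6.1 repeat the rule for PP. The pass/fail criterion in Protocol 7.4 names no population: "Non-inferiority of DM05 versus Optive with a non-inferiority margin set at 2 points on the Oxford score".

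**Role of ITT.** Protocol 7.1.2.2, under sensitivity analysis, says "Same analysis will be performed on ITT population with imputation of values in case of missing data with LOCF technique", and also without imputation. SAP 7.1.2 plans the ITT run unconditionally, but SAP 4.1.1 places it after non-inferiority has been concluded. In SAP 7.6.1 the ITT runs follow a baseline age or sex imbalance, or a treatment-by-centre interaction, and only LOCF is described. The planned tables (SAP 9.1) list ITT non-inferiority only as sensitivity analyses 1 and 2, so no plain ITT non-inferiority table appears. Nothing says what follows if PP passes and ITT fails. The PP conclusion also opens the superiority test.

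**Who leaves PP.** Major deviators are identified at a blind review (Protocol 7.1.1 and 8.1.3.2). Protocol 10.2 also removes subjects with too short a treatment or no evaluation of the main criterion. Subjects are not blinded (Protocol 6.1.2). On reporting, SAP 7.1.1 says "protocol deviations will be summarized in tables, for the whole population".

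**The concern.** Randomisation protects the comparison of all randomised patients. It does not protect a subset formed by what happened afterwards. A subject who knows the product and is doing badly on it may stop early, add another treatment or deviate in some other way. If that happens more in the DM05 arm, the PP difference moves in DM05's favour. The ITT analysis could show the shift, but under the written rule the report would still conclude non-inferiority. The chance of a false non-inferiority claim is then no longer held at its nominal level, and the plan has no rule for discordant results.

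**Working it through.** **Inputs from the documents.**
- Margin: "The clinical non-inferiority margin was set at 2 points on the Oxford score" (Protocol 7.2).
- Size: "Assessing a standard-deviation equal to 2.5, a total of 68 patients (34 patients in each group") for 90% power (Protocol 7.2).
- Error level: "All statistical tests will be 2-tailed with a Type I error of 0.05 unless otherwise stated" (SAP 6.2), with the sample size chosen "to set-up the non-inferiority based on a bilateral confidence interval at 95"% (Protocol 7.2). This is one-sided 2.5% for non-inferiority.
- 80 randomised, 40 per arm, after 15% drop-out.

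**Assumed, because not stated:** a true difference of 0 for the power figure, with 0.5 and 1.0 also shown.

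**1. The plan's own figure.** With 34 per arm, SE = 2.5 × √(2/34) = 0.606 and margin/SE = 2/0.606 = 3.30. The noncentral t gives 90.15% power; 33 per arm gives 89.3%. So 34 per arm is the smallest size that reaches 90%, and 68/0.85 = 80. The figure reproduces with a true difference of 0.

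**2. False non-inferiority under the PP-only rule.** Trials were simulated with t-based 95% intervals on change from baseline, without the baseline covariate. The settings were SD 2.5, true difference 2, 38 per arm with a D35 score and 4 per arm outside PP. The correlation is between leaving PP and a poor change in staining. Ranges show separate runs.

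| How patients leave PP | PP-only rule passes |
|---|---|
| DM05 only, correlation 1 (the 4 worst) | 14.6% to 14.8% |
| DM05 only, correlation 0.5 | 6.0% to 6.3% |
| DM05 only, correlation 0.3 | 4.2% to 4.3% |
| Both arms alike, correlation 1 | 4.0% to 4.2% |
| Both arms alike, correlation 0.5 | 2.7% |

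With both sets required, the pass rate at correlation 1 in DM05 only is 2.4% to 2.5%. This follows directly: P(PP passes and ITT passes) ≤ P(ITT passes), which is 2.5% at a true difference of 2 among all patients with a score.

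**3. A second mechanism.** Forty per arm are randomised, all with a D35 score, and 6 per arm are outside PP. The true difference over all randomised patients is 2, and the excluded DM05 patients are *s* points worse than those retained. The PP difference is 2 − *s* × 6/40, that is 1.7, 1.4 and 1.1 for *s* = 2, 4 and 6. PP alone passes 7.1%, 16.2% and 31.1% of the time; both sets pass 2.1%, 1.6% and 1.1%.

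**4. Cost in power of requiring both sets.**

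| Situation | PP only | Both | Cost (points) |
|---|---|---|---|
| True difference 0, 6 of 40 per arm out at random | 90.2% | 89.4% | 0.8 |
| True difference 0, 4 of 38 per arm out at random | 90.1% | 89.2% | 0.9 |
| True difference 0.5, random | 68.5% | 66.0% | 2.5 |
| True difference 1.0, random | 36.9% | 33.0% | 3.9 (3.5 in another run) |
| True difference 0 in PP, 6 excluded DM05 patients 2 points worse | 90.0% | 82.7% | 7.2 |

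**5. Patients with no D35 score.** They are outside PP and outside observed-case ITT, so the joint rule gives no check on their loss. Carrying the baseline forward scores them as unchanged, even if they were worsening. When the 4 worst DM05 patients were treated this way, PP and LOCF ITT together still passed about 15% of the time.

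**The case against.** A prespecified PP primary analysis with blind review and a supporting ITT run is a coherent choice for non-inferiority, and nothing in the documents obliges the sponsor to make the two sets co-primary. Staining is graded by a masked, independent investigator, and unblinding follows classification of deviations and database lock. These safeguards stand. They limit exclusion chosen by arm. They do not stop an unblinded subject from deviating because of the product.

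A reader might infer more than the documents support in four ways.
- **That the trial's false-positive rate is about 15%.** That figure needs perfect selection on the endpoint in one arm only. At correlation 0.3 to 0.5 it is about 4% to 6%, and if both arms select alike it is close to 4% or lower. Nothing in the documents shows that such selection will occur.
- **That the ITT result is withheld.** Protocol 7.1.2.2 and SAP 7.1.2 plan it, so a discordant result should be visible. The gap is that it has no consequence and that the SAP's detailed section and table list do not carry it through.
- **That exclusions are not shown by arm at all.** SAP 7.1.2 gives population counts by treatment group, SAP 7.2 gives completion by treatment group, and SAP 6.4 compares PP with excluded patients at baseline if numbers allow. What is not stated is the reasons for PP exclusion by arm.
- **That requiring both sets always costs under 1 point of power.** That holds only at a true difference of 0 with balanced exclusions unrelated to outcome.

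**Conclusion.** The point holds as a gap in the decision rule. Non-inferiority rests on PP alone, and no text lets a failing ITT result change it. In the main illustration the PP-only rule passes about 4% to 15% of the time at a true difference equal to the margin, against a nominal 2.5%; the joint rule stays at about 2.5% or less. These rates show what the rule permits and are not a forecast. They rest on SD 2.5, excluded patients who have a D35 score, and selection in the DM05 arm that follows response. ANCOVA adjustment was not simulated; it would reduce the residual SD in both sets and is not expected to change the conclusion. The protection does not extend to patients lost before D35. The change should be made, but the sample size itself is sound on its stated inputs.

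**What to change.** - In Protocol 7.1.2.1 and 7.4 and SAP 4.1.1 and 7.6.1, state: *Non-inferiority is concluded only if the upper bound of the two-sided 95% CI is no higher than 2 in both the PP and the ITT observed-case analyses; otherwise it is not established.* No alpha adjustment is needed, because both must pass.
- Run the plain ITT non-inferiority analysis unconditionally, describe it in SAP 7.6.1, and add its table to SAP 9.1.
- Report the planned LOCF run as supportive, using the value from the withdrawal visit (Protocol 16.3.1) where there is one. Reconcile Protocol 7.10, which applies LOCF to PP and to an undefined FAS, with the observed-case main analysis.
- Tabulate PP exclusions and missing D35 scores, with reasons, by arm. State that the joint rule does not cover patients without a D35 score.

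**Cost.** Protocol and SAP wording and two or three tables, with no extra patients or visits. The loss of power is about 1 point at a true difference of 0 with balanced, uninformative exclusions, about 2.5 points at 0.5, and 3.5 to 4 at 1.0. It is larger when exclusions are informative, which is when the rule is doing its work. This is a cheap improvement.
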